1.3 Exploratory Aims

1.3.1 To characterize tRCC clinical behavior across all age groups.

1.3.2 To evaluate type of antitumor immune response and stability of T cell activation before and after treatment with immunotherapy or antiangiogenic therapy.

1.3.3 To develop a tumor bank of tRCC tumor samples treated on study for further biological investigations.

1.3.4 To characterize the pharmacokinetics of axitinib when given in combination with nivolumab in pediatric patients with tRCC.

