9.2 Study Design

With Amendment 5A, as before, eligible tRCC patients will be randomized to receive either axitinib and nivolumab (Arm A) or nivolumab alone (Arm C) in a 1:1 ratio. The enrolling institutions will assess the initial patient eligibility, including the type of RCC. Randomization will incorporate stratification for age (< 18 years vs. \geq 18 years), and prior systemic therapy for RCC (none, anti-VEGF based therapy, or systemic therapy other than anti-VEGF). Patients may receive their assigned therapy for up to 2 years or 26 cycles of therapy, whichever occurs first, as long as they do not experience either progressive disease as defined by the immune RECIST criteria (see [Section 10.2.5](#)) or unacceptable toxicities. The primary endpoint of this study is progression-free survival (PFS), defined as the time from randomization to the earliest of disease progression (according to RECIST adapted for immunotherapy) or death due to any cause (see [Sections 9.4](#) and [10.2](#)).

In planning the amended 2-arm design of this study, patient-level data on tRCC patients with metastatic disease who would have been eligible for AREN1721 were extracted from three separate cohorts: 7 patients from the cohort described by Ambalavanan and Geller, 15 patients from the cohort described by Malouf et al, and 3 patients from the COG study AREN03B2.^{34,24} PFS for the 3 cohorts was plotted together and found to be in agreement (log-rank test $p = 0.72$; Figure 1A). As such, these data were pooled into a single “historical” cohort used to select an appropriate parametric distribution for PFS in this disease setting from the proportional hazards family of models, from which determinants of power and sample size could be based. Upon superimposing the “best-fit” exponential, Weibull, and piecewise exponential models onto the Kaplan-Meier plot for PFS in the pooled historical cohort, it was determined that the piecewise exponential model offered a practically superior fit warranting the relative increase in model complexity (Figure 1B):

Figure 1A

[figure not shown]
[figure not shown]

Figure 1B

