A comprehensive simulation study was then performed, varying the following: the target sample size and maximum number of events required at the final analysis time point, the number and timing of interim analyses for futility, futility stopping strategies (conditional power under the alternative and current HR), and the true underlying hazard ratio (from $HR = 1.0$, the null hypothesis type I error scenario, to $HR = 0.40$, the target alternative hypothesis scenario). For all settings and strategies evaluated in simulations, accrual was assumed to be uniformly distributed as 24 patients per year (as reasoned above, acknowledging that slower than expected accrual will yield greater statistical power than reported here). PFS in the control arm was assumed to follow the piecewise exponential distribution shown in Figure 1B. With 100,000 replicates (simulated trials) used to assess each scenario, we arrived at the following trial design and set of operating characteristics.

The trial will enroll a target of 28 patients to observe 22 PFS events, which are required to achieve at least 80% power to detect a hazard ratio of $HR=0.40$ using a one-sided stratified log-rank test with $\alpha = 0.15$. If stratum-specific sample sizes allow, stratification of the test will include those factors used for stratification at the time of randomization (age and prior systemic therapy).

The trial will include one formal interim analyses for futility, conducted at 50% (11) of the required 22 PFS events. At this time, an observed hazard ratio greater than 1.00 (i.e., a

trend in the wrong direction) will result in early termination of the trial for futility. The simulated percentage change of early stopping for futility at the planned interim analysis (“early futility”), continuing to the final analysis but failing to reach statistical significance (“lack of efficacy”), and continuing to the final analysis and reaching statistical significance (“efficacy”) are tabled below for a range of true underlying hazard ratios. Also presented are the average simulated sample size (“Average N”) and average simulated time from reopening with Amendment 5A to final trial outcome (“Average Remaining Duration”) corresponding to each possible trial outcome. These numbers take into account the patients already enrolled, eligible, and anticipated to be evaluable for the primary endpoint.

True HR	Interim Analysis (50% Events)			Final Analysis (100% Events)			

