ORR: A logistic regression model for overall response, stratified by the stratification factors used at randomization (age and prior therapy) will be fit, including treatment arm as a key covariate. From this model, the odds ratio for treatment arm will be reported with a 70% confidence interval. The ORR observed within each treatment arm will also be reported.

OS: A stratified, one-sided log-rank test (using the stratification factors at randomization, age and prior therapy) will be performed to compare treatment arms with alpha = 0.15. Cox proportional hazards models will also be fit to evaluate the final hazard ratio between the treatment arms, with exploratory modeling taking into account the potential influence of other factors (e.g., baseline disease burden, upfront vs. delayed nephrectomy). From these models, the hazard ratio for treatment assignment will be reported with a 70% confidence interval (to align with the overall alpha level of the primary log-rank test).

AEs: All Grade 3 or higher non-hematologic toxicities and all Grade 4-5 adverse events occurring during protocol therapy or within 100 days of treatment discontinuation, including crossover for patients who receive crossover combination therapy, will be analyzed. The rates of these events will be reported separately by treatment arm (including crossover as a “3rd” arm for this purpose), and both by individual AE and class of AE (e.g., hematologic). Given that some AEs may be rare, Fisher Exact tests will be used to test for statistical significance among any apparent differences by treatment arm.

Exploratory Analyses

Exploratory Aim 1.3.1: To characterize tRCC clinical behavior across all age groups.
We will list and summarize the frequency of site(s) of disease at presentation (including extent of lymph node involvement), site(s) of relapse, surgical practices on protocol therapy, and radiotherapy practices on protocol therapy. We will also summarize the overall response rate (ORR) submitted by the enrolling institution.

Exploratory Aim 1.3.2: To evaluate type of antitumor immune response and stability of T cell activation before and after treatment with immunotherapy or antiangiogenic therapy.

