We will summarize the levels of analytes and tumor expression before and after treatment and evaluate the changes due to treatment after logarithmic transformation using the paired t-test. Analytes include myeloid derived stem cells (MDSC): CD45, CD11b, CD33, CD14, CD15, HLA-DR, viability, stain 1; Tregs: viability, CD45, CD4, CD3, CD24, FoxP3; CD8 T cells (CD45, CD8, CD3); CD8 phenotype and activation and exhaustion (CD69, CD38, PD1, CD244, TIM3). Tumor expression of PDL-1, PD1, CD3, CD4 and CD8 will be assessed using TFE RCC samples from the study and scored for intensity (0 – 3).

Exploratory Aim 1.3.4: To characterize the pharmacokinetics of axitinib when given in combination with nivolumab in pediatric patients with tRCC.

The population PK analysis will include all treated patients enrolled beyond Amendment 5A who have at least 1 concentration above the below limit of quantitation (BLQ) in patients treated with axitinib. Pooled PK analysis with another study is to explore the effect of age and body size on axitinib CL/F and Vd/F and make predictions on the dosing of axitinib in pediatric patients in different age groups. Exposure-response relationships will also be explored. The results will be reported separately in a population modeling analysis report. For the purposes of PK analysis, patients who receive crossover therapy will be reported both as a separate cohort and pooled with patients receiving combination therapy up front.

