13.1.2 Cytoreductive Nephrectomy

Cytoreductive nephrectomy is not required for patient enrollment; however, we encourage cytoreductive nephrectomy when feasible. Level I evidence from the prior immune-modulatory era (cytokine era) for treating metastatic renal cell carcinoma demonstrated the survival benefit of cytoreductive nephrectomy.^{64, 65} While we await randomized-trial data about the impact of cytoreductive nephrectomy in the current era of targeted therapy for metastatic renal cell carcinoma, analyses of retrospective and administrative data suggest that it may be beneficial in select patients.^{66, 67} Therefore, when possible we would encourage cytoreductive nephrectomy prior to beginning protocol therapy. Per [Section 3.2.8.3](#), patients must be more than 7 days out from major surgery (which includes open or laparoscopic nephrectomy) for eligibility. For the purposes of this study cytoreductive nephrectomy may include radical or partial nephrectomy and may be achieved by either an open or laparoscopic approach. Additionally, delayed cytoreductive nephrectomy is permitted 12 weeks after starting protocol therapy, taking into account the need for holding axitinib before and after nephrectomy per [Section 13.1.8.3](#).

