15.2.1 Immunotherapy Biomarkers in Blood

15.2.1.1 Specimens

In consenting patients, peripheral blood will be acquired (15-20 mL per sample) in green top sodium tubes at the following timepoints:

- Before treatment initiation
- Before Day 1 of Cycles 2, 3, and 9 (within 72 hours prior to Day 1 dosing)
- Within 3 weeks after the last dose of study treatment

Lithium heparin tubes are also acceptable if a site is unable or unwilling to obtain green top sodium tubes due to cost or availability.

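### The paired t-test for exploratory Aim 1.3.2 shows change from baseline, not change caused by treatment, and the plan names no comparison of the randomised arms

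*Combined protocol and SAP*

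**What the plan says.** Section 1.3 words the aim as "To evaluate type of antitumor immune response and stability of T cell activation before and after treatment with immunotherapy or antiangiogenic therapy". Section 9.3 then promises before-and-after summaries of analytes and tumor expression, and says it will "evaluate the changes due to treatment after logarithmic transformation using the paired t-test". That is the whole inferential plan for the aim. It does not say whether arms are pooled or analysed separately, which on-treatment sample counts as the later one, or how concurrent treatment is handled.

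Other parts of the plan do use the arms. Section 9.2 randomises patients to axitinib plus nivolumab or "nivolumab alone (Arm C) in a 1:1 ratio". In Section 9.3 the response-rate model is fitted "including treatment arm as a key covariate", and for adverse events "The rates of these events will be reported separately by treatment arm".

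Section 15.2.1.1 schedules blood, in consenting patients, before treatment, before Cycles 2, 3 and 9, and within three weeks of the last dose. Section 15.2.2.1 limits on-treatment tumor tissue to samples taken for a clinical reason.

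**The concern.** Section 9.3 attributes the change to treatment, but the paired t-test has as its null a mean within-patient log change of zero. Rejecting it shows that values changed. It does not show why.

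The protocol itself allows several causes other than the study drugs:

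- **Surgery.** Section 13.1.2 states that "when possible we would encourage cytoreductive nephrectomy prior to beginning protocol therapy". Section 3.2.8.3 excludes major surgery only within 7 days before enrollment, and Section 3.1.5 has therapy start within 5 days after it. A baseline sample can therefore fall little more than a week after a nephrectomy.
- **Washout.** Sections 3.2.6 and 3.2.8.3 allow enrollment 7 days after a biologic agent and 2 weeks after myelosuppressive chemotherapy or a targeted small molecule.
- **Concurrent care.** Section 4.2 permits steroids, small-port radiotherapy and surgery during therapy.
- **Disease course and selection.** Cycle 9 samples exist only for patients still on therapy, and Arm C patients may have added axitinib by then.

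At stake is a statement that treatment induced an immune change when the analysis cannot show it. Such a statement could mislead later work in a rare disease.

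**Working it through.** **No plan figure to reproduce.** The documents give no sample size, alpha, SD, effect size or power for Aim 1.3.2.

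**Inputs from the documents.** Section 9.2: "The trial will enroll a target of 28 patients to observe 22 PFS events". With 1:1 allocation, 28/2 = 14 per arm, which is roughly the most that can be expected because sampling is optional.

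**Assumptions, not in the documents.** Two-sided alpha 0.05; normal log values; before/after correlation 0.5; 10 to 28 pairs; drift of 0 to 1.0 SD. At correlation 0.5 the SD of the log change is √(2 × (1 − 0.5)) = 1 times the SD of a log value, so both scales share one unit.

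**Step 1: what the paired test sees.** Write the mean log change as drug effect τ plus drift δ. The test statistic is the mean change divided by (SD of change/√n). Its noncentrality is (τ + δ)√n/SD, so it responds to the sum and cannot tell the parts apart.

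**Step 2: rejection when τ = 0.** The probability is that a noncentral t with n − 1 df and noncentrality δ√n exceeds the critical value in either direction. For δ = 0.5:

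- n = 14: 0.5 × √14 = 1.87, critical value 2.16, rejection 41%.
- n = 20: 0.5 × √20 = 2.24, critical value 2.09, rejection 56%.
- n = 28: 0.5 × √28 = 2.65, critical value 2.05, rejection 72%.

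| Pairs | δ = 0 | 0.25 | 0.5 | 0.75 | 1.0 |
|---|---|---|---|---|---|
| 10 | 5% | 11% | 29% | 56% | 80% |
| 14 | 5% | 14% | 41% | 74% | 93% |
| 28 | 5% | 25% | 72% | 97% | 99.9% |

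At δ = 0.3 the rates are 18%, 25% and 33% with 14, 20 and 28 pairs. A simulation of 40,000 replicates with 28 pairs agrees with the last row of the table.

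**Step 3: what the arm comparison sees.** Let nivolumab contribute ν and added axitinib contribute α. Mean change is ν + α + δ in Arm A and ν + δ in Arm C, so the difference is α. Common drift cancels, and so does nivolumab. In simulation with 14 per arm, the between-arm test rejects about 5% of the time at every common drift from 0 to 1.0 SD.

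**Step 4: its precision.** Adjusting for baseline leaves a residual SD of √(1 − 0.5²) = 0.866. For a 1 SD effect the noncentrality is about (1/0.866) × √(n/2), which is 2.16, 2.58 and 3.06 with 7, 10 and 14 per arm. Power is about 48%, 67% and 83%, moving a point or two with how chance baseline imbalance is handled. An unadjusted comparison of log change gives 72% for 1 SD and 25% for 0.5 SD with 14 per arm, and 41% for 1 SD with 7 per arm.

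**Step 5: timing.** Cycle 3 Day 1 comes after 2 × 4 = 8 weeks. That is inside the 12 weeks in which Section 13.1.8.1 bars tumor resection, and close to the first scheduled tumor evaluation after Cycle 2. The Cycle 2 and 3 draws therefore largely precede crossover and selection by outcome.

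**The case against.** The strongest reply is that the method fits the aim. Section 1.3 asks a before-and-after question, Section 2.4 speaks of longitudinal assessment, and a paired test answers that. Both open arms receive nivolumab, so no randomised contrast isolates PD-1 blockade, which is the main interest in Section 2.4. The antiangiogenic wording also fits the original three-arm design, and Arm B patients followed the same biomarker schedule. All of this stands. It is why the paired analysis should stay and only its attribution should go.

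Three stronger readings are tempting, and the documents do not support them.

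- A reader might infer that the paired test would hide a real axitinib effect. If axitinib adds 1 SD and a common shift takes away 0.5 SD, the arm means are +0.5 and −0.5, and a pooled mean is exactly zero. That needs pooling, which Section 9.3 does not state, and a cancellation chosen to be exact.
- A reader might infer that Arm A versus Arm C should become the main analysis. It answers a narrower question than the aim poses.
- A reader might infer that end-of-treatment samples come from a group selected by outcome. They are scheduled for every consenting patient; only their timing depends on outcome.

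It is also fair that the drift is assumed. Prior nephrectomy is encouraged, not required, so recovery would affect only some patients, by an unknown amount.

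**Conclusion.** The point holds in limited form. The planned test supports a statement about change from baseline and does not support the attribution to treatment in Section 9.3. Running it separately by arm does not cure this, because each within-arm test has the same null. The remark that no arm comparison is planned rests on the plan's silence for this aim.

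The logical point needs no assumption. Its size does: the 41% to 72% false-attribution rates apply only if a common drift of 0.5 SD exists and 14 to 28 pairs are available.

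Randomisation offers a partial remedy. It gives an unconfounded answer about adding axitinib to nivolumab, imprecisely, and none about nivolumab itself. The aim is exploratory, and the primary PFS analysis does not depend on it. Importance is modest, but the correction is cheap and worth making.

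**What to change.** In Section 9.3, under Aim 1.3.2:

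1. Replace the attribution to treatment with *change from baseline on treatment*, and report the paired analysis by arm.
2. For blood analytes, add a randomised Arm A versus Arm C comparison of log values at Cycle 2 Day 1 and Cycle 3 Day 1, by ANCOVA with log baseline as covariate or by one mixed model over both visits. Name it as the only analysis that supports a causal statement, limited to adding axitinib to nivolumab.
3. Keep the within-patient analysis for the before-and-after question, including nivolumab and any Arm B samples, without causal attribution. Tumor-tissue pairs belong here too.
4. Treat Cycle 9 pairs as descriptive, because they come from patients still on therapy who may have crossed over. Treat end-of-treatment pairs as descriptive, because their timing depends on outcome.

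The cost is one paragraph of text, with no new samples or patients. The downside is the limited precision of the arm comparison, which should be reported with confidence intervals.

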9.4 Endpoints and Evaluability

The primary endpoint is progression-free survival (PFS), which is defined as the time from randomization to the earliest occurrence of disease progression (as defined by modified RECIST criteria for immunotherapy, described in [Section 10](#)) or death due to any cause among patients who initiated protocol treatment. Patients not experiencing a PFS event by the time of a prospectively-planned interim or final analysis will be right-censored at the time of their most recent response/progression evaluation. Following the intent-to-treat principle, all patients who are randomized and confirmed to have tRCC by central pathology review will be evaluable for PFS. Patients randomized to Arm B prior to Amendment 2A, and patients who have a central path review confirming a diagnosis other than tRCC, or who never receive central path review per protocol, will be considered inevaluable for the primary endpoint comparison but included in study descriptive statistics.

The overall response rate (ORR) will be defined as the rate of complete or partial responses (assessed by imaging) among patients who initiated protocol therapy and completed at least one subsequent imaging assessment. Patients who are randomized to Arms A or C and are confirmed to have tRCC by central pathology review will be evaluable for ORR.

Overall survival (OS) will be calculated as the time from randomization to death due to any cause, with surviving patients being right-censored at their length of follow-up at the time of analysis. Patients who are randomized to Arms A or C and are confirmed to have tRCC by central pathology review will be evaluable for OS.

Note: For calculations of both PFS and ORR, any lesions resected during protocol therapy for reasons other than progression (as noted by sites or documented upon central surgical review) will not contribute toward response/progression assessments. Response/progression assessments are scheduled to take place after Cycles 2, 4, 6, 9, 12, and then every 4 cycles thereafter, after every cycle following any suspected pseudoprogression until the total tumor burden subsequently diminishes, or at any time clinical progression is suspected. Once in follow-up, patients without a documented PFS event will be evaluated according to the schedule in [Section 7.2](#). ORR and OS will be analyzed as a part of exploratory aim 1.3.1.

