3.2.3 Diagnosis

Histologically confirmed unresectable or metastatic translocation morphology renal cell carcinoma diagnosed using WHO-defined criteria. Patients may be newly diagnosed or have received prior cancer therapy.

3.2.3.1 Patients must have had histologic verification of the malignancy.

3.2.3.2 Patients must have measurable disease, documented by clinical, radiographic, or histologic criteria as defined by RECIST v1.1.

3.2.3.3 Patients must have a tumor showing the appropriate morphologic appearance, and either confirmed TFE3 nuclear protein expression by immunohistochemistry with appropriate positive and negative controls performed at a CLIA-certified laboratory, or evidence of TFE3 or TFEb translocation by either FISH or RT-PCR performed at a CLIA-certified laboratory. For TFE3 immunohistochemistry, any nuclear positivity in the presence of appropriate positive and negative controls should be considered as evidence of TFE3 immunohistochemical expression.

NOTE: If the institution is unable to perform these studies, unstained slides may be submitted to [name], who will perform TFE3 analysis at no charge. The slide will be returned to the referring institution for local evaluation, to be included in their institutional report. See [Section 14.1.2](#) for complete details.

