9.0 STATISTICAL CONSIDERATIONS

9.1 Sample Size and Study Duration

As of Amendment 5A, which now allows crossover upon progression from the nivolumab arm to the nivolumab + axitinib arm, we expect enrollment of approximately 2 patients per month. This is derived from tRCC prevalence, access to treatment centers, and enrollment patterns to date, which should be aided by the crossover.

To reduce the overall sample size from the prior design, we have maintained the same overall study design but changed two design parameters: 1-sided alpha will be increased from 0.05 to 0.15, and the targeted hazard ratio will be reduced from $HR = 0.50$ to $HR = 0.40$. With these changes, 22 PFS events will be required to address the primary objective comparing Arms A and C at the time of final analysis (see [Section 9.2](#)). Allowing that approximately 25% of eligible and evaluable patients may not have experienced a PFS event by the time of the final analysis, the target accrual on this study is 28 patients. To account for an additional estimated 5% of patients who might be found to be ineligible for the study or inevaluable for the primary endpoint at the time of or following study enrollment (e.g., due to randomization to Arm B, no central path review performed, or having central path review confirming a diagnosis other than tRCC), the ceiling accrual will be set to 40 patients, including those patients already enrolled.

If the study accrues to the target accrual without interim stopping for futility, the additional time required to enroll up to this maximum once re-opening under Amendment 5A is estimated to be 14 months. As before, all eligible patients will be followed for 5 years after randomization, and the final analysis will be conducted once the target number of PFS events needed for the final analysis has been reached, or after 2 years of follow-up is obtained for the last patient enrolled, whichever occurs first.

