14.2 Tissue Specimens/Pathology Review at Time of Diagnosis

All patients enrolling on this protocol require institutional histological confirmation of translocation-renal cell carcinoma and institutional confirmation of either robust TFE3 nuclear protein expression by immunohistochemistry or evidence of TFE3 or TFEb translocation by either FISH or RT-PCR in a CLIA-certified laboratory. **Sites are required to submit tumor samples within 4 weeks of initiating protocol therapy, and are encouraged to submit tumor samples at second look surgery, relapse, or autopsy.** All reviews are retrospective and results from the reviews will not be returned to the submitting institution.

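### Section 9.4 drops from the primary PFS comparison any randomized patient who never has central pathology review, although it invokes intent-to-treat and entry already requires an institutional tRCC diagnosis

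*Combined protocol and SAP*

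**What the plan says.** **Entry.** The enrolling institution makes the diagnosis (9.2). Section 3.2.3.3 requires appropriate morphology plus either TFE3 nuclear staining or a TFE3/TFEb translocation from a CLIA-certified laboratory. Central review plays no part in entry.

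**Central review.** It is retrospective, covers all enrolled patients, and its result does not go back to the site (14.1.1). Section 13.3 makes submission compulsory, and 14.2 sets the deadline: "Sites are required to submit tumor samples within 4 weeks of initiating protocol therapy".

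**Analysis sets.** Section 9.4 appeals to intent-to-treat but defines the PFS set as patients both randomized and centrally confirmed. Besides Arm B patients and those with another diagnosis on review, it excludes patients "or who never receive central path review per protocol, will be considered inevaluable for the primary endpoint comparison"; they appear only in descriptive statistics. The OS and ORR sets in the same section also require central confirmation.

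**Sample size.** Section 9.1 gives "no central path review performed" as one example of the losses covered by a 5% allowance. It also states that "22 PFS events will be required to address the primary objective comparing Arms A and C", and that "the target accrual on this study is 28 patients", with a ceiling of 40.

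**The concern.** Two different exclusions sit in one sentence of 9.4. A non-tRCC reading of diagnostic tissue uses information that existed before randomization. A missing review reflects what the site did afterwards. Arm A adds an oral drug to the infusion and no placebo or blinding is described, so the site knows the arm when it sends slides, or does not.

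If missing review is related to both arm and early outcome, the A-versus-C comparison is no longer protected by randomization, and pre-specifying the exclusion does not change that. The patients removed already have a CLIA-supported institutional diagnosis, and no other comparative efficacy analysis brings them back.

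One group has no submission deadline at all. A patient who is randomized but never starts therapy, for example after a failed laboratory recheck (3.2, 8.1n), never starts the 14.2 clock. Section 9.4 also gives no date at which a review counts as never received.

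**Working it through.** **1. Timing of the deadline.** Therapy is projected to start at most 5 days after enrollment (3.1.5), and slides are due within 4 weeks of that start: 5 + 28 = day 33 at the latest. The first scheduled disease evaluation follows Cycle 2 (4.1): 2 × 28 = 56 days of therapy. A compliant site therefore sends slides before any scheduled progression assessment. Only death or clinically suspected progression could come first.

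**2. The plan's own figures.** Inputs from 9.1 and 9.2: one-sided alpha 0.15 ("1-sided alpha will be increased from 0.05 to 0.15"), 22 events, 1:1 allocation, HR 0.40, and a stop at 11 events if the observed HR exceeds 1.00. The plan says that 22 events are "required to achieve at least 80% power to detect a hazard ratio of $HR=0.40$ using a one-sided stratified log-rank test".
- Freedman drift per root event: (1 − 0.40)/(1 + 0.40) = 0.4286.
- Without the interim: Φ(√22 × 0.4286 − 1.036) = Φ(0.974) = 83.5%.
- Early futility at HR 0.40: Φ(−√11 × 0.4286) = Φ(−1.421) = 7.8% (plan: 8%).
- With the futility stop (bivariate normal, correlation √0.5): 81.0% power (plan: 80%).
- Under HR 1.0: 50% early futility and 13.9% efficacy (plan: 50% and 14%).

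The stated design is reproduced.

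**3. Effect of losing unreviewed patients.** Two simulations used exponential PFS and an unstratified one-sided log-rank test at 0.15. The plan's piecewise control curve is in a figure not shown, so the exponential form is an assumption.
- *Simulation 1:* 14 per arm, 22 events, no interim, 40,000 trials per cell. The one or two earliest PFS times in one arm are deleted.
- *Simulation 2:* accrual 24 per year, futility look at 11 events, 28 evaluable patients and 22 events maintained by replacement, control median 6 months (2.1.1 cites 5–8 months for pediatric anti-VEGF therapy), 10,000 trials. Up to one or two patients with an event before 2 months are deleted from one arm.

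| Scenario (one / two lost) | Simulation 1 | Simulation 2 |
|---|---|---|
| HR 1.0, no loss: positive result | 15.5% | 14.1% |
| HR 1.0, early Arm A events lost | 20.7% / 26.4% | 20.1% / 24.2% |
| HR 1.0, early Arm C events lost | 11.8% / 8.6% | 10.8% / 8.1% |
| HR 1.0, random loss | 15.1–15.8% | 13.9% / 13.7% |
| HR 0.40, no loss: power | 85.5% | 82.8% |
| HR 0.40, early Arm C events lost | 82.8% / 79.4% | 78.9% / 74.9% |
| HR 0.40, random loss | not tabulated | 82.7% / 82.9% |

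Power losses from early Arm C events are 85.5 − 82.8 = 2.7 and 85.5 − 79.4 = 6.1 points in simulation 1, and 82.8 − 78.9 = 3.9 and 82.8 − 74.9 = 7.9 points in simulation 2. In simulation 2, early futility stopping at HR 0.40 also rises, from 7.4% to 10.3% or 12.8%.

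**4. The 5% allowance.** 28/0.95 = 29.5, so 30 patients: room for one or two losses from all causes together. The ceiling of 40 protects the event count but not against selective loss.

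**The case against.** The strongest reply is that selective loss is unlikely. Submission is compulsory, earlier submission is not barred, and the deadline falls before the first scheduled scan. The material is archived diagnostic tissue (14.3), so the patient need not be present, and patients off therapy remain in follow-up (8.1). Nothing in the documents shows that submission tracks arm and outcome. Wanting central confirmation is also reasonable when 3.2.3.3 accepts any nuclear TFE3 positivity. All of this stands, and it limits the size of the concern.

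Three stronger readings are tempting but unsupported:
- *Slides are sent only once treatment is under way.* Section 14.2 sets a latest date, not an earliest one.
- *The plan expects one or two missing reviews.* The 5% in 9.1 pools every ineligible or inevaluable patient, and missing review is only one example.
- *The real type I error is close to double the nominal 0.15.* The 20–26% figures come from deleting early events in one chosen arm. They are not forecasts.

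The reply does not answer why a patient with a qualifying institutional diagnosis should leave every efficacy comparison when a site fails to comply, or what happens to never-treated patients. One limit of the remedy also stands: a true non-tRCC patient is dropped if slides arrive and kept if they do not, so some dependence on submission remains.

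**Conclusion.** The concern holds in a limited form. The primary set in 9.4 is not intent-to-treat for patients without central review, and no planned comparative efficacy analysis keeps them. The likely bias is small. The worst-case range is a false-positive chance of about 20–21% for one lost early Arm A event and 24–26% for two, against about 14–15% with none. For early Arm C losses, power at HR 0.40 falls by about 3–4 points for one and 6–8 points for two. Random loss does almost nothing.

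These figures assume exponential PFS, an unstratified test and loss concentrated on early events in one arm. The number of reviews actually missing, and its split by arm, cannot be known from the documents. The case for change rests on the cost of the remedy being almost nil, not on evidence that bias has occurred.

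**What to change.** In 9.4, keep every patient randomized to Arm A or C evaluable for PFS and OS unless central review of pre-randomization tissue, done blind to arm and outcome, returns a diagnosis other than tRCC. Where review is missing, let the institutional diagnosis required by 3.2.3.3 stand. Run the centrally confirmed set as a sensitivity analysis and report missing reviews by arm. In the same edit, reconcile the phrase in the PFS definition that limits it to patients who began protocol treatment, since it also bears on never-treated patients.

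The cost is wording. The 22 events, the target of 28 and the operating characteristics in section 9.2 are unchanged. The small downside is that an occasional unreviewed patient may not have tRCC, which slightly dilutes the effect; the sensitivity analysis shows by how much.

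Two further changes are not worth making. A tissue-availability criterion in 3.2.3 would add an entry barrier in a rare disease expected to accrue about 2 patients a month. Timing submission from enrollment would move the deadline by at most about 5 days for treated patients.
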